5.7.1.1. Sensitivity Analyses

Robustness of the primary analyses results in Cohort A and Cohort B will be assessed through sensitivity analyses as follows:

Sensitivity analysis by excluding subjects who develop asymptomatic or symptomatic SARS-CoV-2 infection within 72 hours of the study drug administration

This analysis assesses for the sensitivity of the results to subjects who may have had undetected infections prior to dosing. That is, a subject had any onset of a positive RT-qPCR within 72 hours of the study drug administration will be excluded for this sensitivity analysis.

This sensitivity analysis will only be performed for Cohort A primary endpoint.

Sensitivity analysis by excluding subjects from non-good clinical practice (GCP) Compliant Site(s)

To access the impact of sites that had non-GCP compliance issues on the primary efficacy points, the primary analyses will be performed by excluding non-GCP compliant site(s).

This sensitivity analysis will be performed for both Cohort A and Cohort B primary endpoints.

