13. Samples for drug concentration and, immunogenicity, and laboratory testing will be collected based on the subject subset designation as indicated in [Table 4](#)
14. The serology test results will not be communicated to the sites. The sponsor's blinded study team will not have access to post-baseline results associated with subject identification until after the database is locked.
15. During each scheduled or unscheduled visit/contact, the investigator or designee will query subject about AEs in general (see Section [10.1.1](#)) and evaluate if the AEs are associated with SARS-CoV-2 infection, including fever (see Section [9.2.2.2](#)). The investigator should recommend that subjects (themselves or by their parent/guardian) measure their temperature daily during EAP, approximately at the same time, and also every time when the subject feels feverish, chills, or sick. Subjects with symptomatic SARS-CoV-2 infection should be queried on their symptoms weekly until symptoms resolve, even during follow-up period, then follow the regular schedule.
16. The information for the household assessment, including household members who receive an EUA approved monoclonal antibody treatment for COVID-19 or household members participating in the R10933-10987-COV-2067 study, should preferably be collected at the baseline visit. There will be a follow-up assessment at day 29.
17. All subjects will have a weekly NP swab sample collected during the EAP. Only subjects who are RT-qPCR positive will continue to have weekly NP swab samples collected during the follow-up period until 2 consecutive negative ( $\geq 24$  hr) RT-qPCR results or the end of study visit.
18. Only for RT-qPCR positive subjects (cohort A and cohort B): Complete assessments from the time the subject first becomes RT-qPCR positive or from the time they develop symptoms suspected to be COVID-19 (later confirmed by RT-qPCR positive results) until the subject has had 2 negative tests or COVID-19 related symptoms have resolved (whichever lasts longer), or until the end of study visit.

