##### **Sensitivity analysis by excluding subjects who develop asymptomatic or symptomatic SARS-CoV-2 infection within 72 hours of the study drug administration**

This analysis assesses for the sensitivity of the results to subjects who may have had undetected infections prior to dosing. That is, a subject had any onset of a positive RT-qPCR within 72 hours of the study drug administration will be excluded for this sensitivity analysis.

This sensitivity analysis will only be performed for cohort A primary endpoint.

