6.4. Windows for Analysis Time Points

Data analyzed by-visit-analysis will be summarized by the scheduled visit described in protocol section 9.1 Schedule of Events. Below are the definitions for the visit windows programmatically imposed on all available measures from unscheduled visits collected over the course of the study including early termination visit and end of study visit. No analysis visit windows will be applied for the study scheduled visits nor for drug concentration and immunogenicity data.

The visit windows are constructed using ranges applied to the number of days in study (study days) when the measure is collected. Below are the relevant definitions for the analysis visit windows:

1. The first study treatment occurs on Study Day 1.
2. Study day is defined as the number of days since the first study treatment administration+1.
3. Since the protocol specifies that measurements be collected before study treatment is administered on a given day, it is appropriate that baseline include Day 1.
4. For randomized but not treated subjects, Day 1 is the day of randomization.

Table 4: Efficacy Analysis Windows for Unscheduled Visits with RT-qPCR or Viral Load Results

Visit Label	Targeted Study Day	Analysis Window in Study Day
Baseline	1	≤ 1
Week 1	8	[2, 11]
Week 2	15	[12, 18]
Week 3	22	[19, 25]
Week 4	29	[26, 32]
Week 5	36	[33, 39]
Week 6	43	[40, 46]
...
Week x	$29+7x$	$[26+7(x-4), 32+7(x-4)]$

If a subject has multiple efficacy assessment visits within an analysis visit window, the one with worst result (e.g., the positive test result will be used for analysis if one record is positive and the other one is negative; the highest viral load result will be used if multiple viral load results are in the same analysis window.) will be selected. If the test results are all negative, the value of the latter visit will be used. If there are multiple positive RT-qPCR results within an analysis window, the record with the highest quantitative result will be used.

Table 5: Global Analysis Windows for Data Other Than RT-qPCR Test

Visit Label	Targeted Study Day	Analysis Window in Study Day
Baseline	1	≤ 1
Day 2	2	[2, 2]
Day 4	4	[3, 4]
Week 1	8	[5, 11]
Week 2	15	[12, 18]
Week 3	22	[19, 25]
Week 4	29	[26, 42]
Week 8	57	[43, 70]
Week 12	85	[71, 98]
Week 16	113	[99, 126]
Week 20	141	[127, 154]
Week 24	169	[155, 182]
Week 28	197	[183, 210]
Week 32	225	≥ 211

Unscheduled Assessments

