10.4. Example of SAS Procedures for Primary Analysis and Missing Data Imputations by FCS

Primary Analysis - GEE Model

Below is an example of SAS code using a generalized linear model to estimate the odds ratio between the treatment groups with the generalized estimation equation (GEE) approach after 100 imputations.

```
proc genmod data=DATA_IN;
class treatment(ref='0') Age_group region; /*eg.treatment= 0:placebo */
by _imputation_;
model response(event='1') =treatment region age_group/dist=bin link=logit;
repeat subject=household_id/type=cs;
lsmeans treatment/diff om cl ilink;
ods output diffss=logOR geeexchcorr=icc;
run;
```

Primary Analysis - Logistic Regression Model

Below is an example of SAS code using a logistic regression model instead of using GEE approach when the percentage of households with a single study subject is 70% or more to estimate the odds ratio between the treatment groups after 100 imputations.

```
proc genmod data=DATA_IN descending;
class treatment(ref='0') Age_group region;
by _imputation_;
model response(event='1') =treatment region age_group/dist=bin link=logit;
lsmeans treatment/diff om cl ilink;
ods output diffss=logOR ParameterEstimates=parameterestimates;
```

run;

Missing Data Imputations – FCS

Assume the missing RT-qPCR test results occurred across Visit 5 (Day 8) to Visit 8 (Day 29) (e.g. 1=positive vs 0=negative). An example of SAS code for FCS MI with the random seed=2069 is presented below.

```
proc mi data=DATAIN out=DATAOUT seed=2069 nimpute=100;
class treatment age_group region v5 v6 v7 v8;
var treatment age_group region v5 v6 v7 v8;
fcs logistic(v5/LIKELIHOOD=AUGMENT);
fcs logistic(v6/LIKELIHOOD=AUGMENT);
fcs logistic(v7/LIKELIHOOD=AUGMENT);
fcs logistic(v8/LIKELIHOOD=AUGMENT);
run;
```

After FCS MI to generate 100 complete datasets, each subject's overall RT-qPCR test status during the EAP can be determined by any of imputed value V5 to V8 is equal to 1. The same model using GEE approach or logistic regression for the primary analysis will be applied.

The results from the 100 analyses will be combined using Rubin's formulae through PROC MIANALYZE procedure shown below.

```
proc mianalyze data=logOR;
ods output parameterestimates=final_logor;
modeleffects estimate;
stderr stderr;
run;
```

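### The 72-hour sensitivity analysis is triggered only by swab date, and no swab is scheduled in that window, so it is a weak check for infection already present at dosing

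*SAP*

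**What the plan says.** SAP 5.7.1.1 and protocol 11.4.3.1.1 describe this analysis in the same terms. The SAP heading is a sensitivity analysis by "excluding subjects who develop asymptomatic or symptomatic SARS-CoV-2 infection within 72 hours of the study drug administration". The stated purpose is to examine the influence of "subjects who may have had undetected infections prior to dosing". The sentence that then defines the analysis excludes a subject with "any onset of a positive RT-qPCR within 72 hours of the study drug administration will be excluded"; it does not mention a symptom date. The scope is narrow: "This sensitivity analysis will only be performed for Cohort A primary endpoint", and that endpoint is symptomatic infection.

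On testing, protocol 9.1.1 (footnote 17 to Table 3) states: "All subjects will have a weekly NP swab sample collected during the EAP". Table 3 places the post-baseline swabs at days 8, 15, 22 and 29, with a window of ±1 day at day 8 and ±3 days afterwards. SAP Appendix 10.4 treats the same four visits as the complete set of scheduled results ("Assume the missing RT-qPCR test results occurred across Visit 5 (Day 8) to Visit 8 (Day 29"). The extra sentinel visits on days 2 to 4 carry no swab.

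Protocol 9.2.2.2 takes the onset date of a symptomatic infection to be the date of its first sign or symptom.

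**The concern.** The heading, the purpose and the rule do not describe the same set of subjects. The heading covers infections with and without symptoms, and the purpose is to catch infections that the baseline swab missed. The rule depends on when a positive swab happens to be taken, and the schedule offers none in the relevant period.

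The question is a live one in this trial. Subjects are randomized within 96 hours of the index case's positive sample, and protocol 3.2.1 puts incubation at about 2 to 14 days. Some cohort A subjects may therefore have been infected, but still PCR negative, when dosed. Whether the effect reflects prevention of new infection or early treatment of incubating infection bears on how the primary result is described. If the analysis removes few of those subjects, its estimate will sit close to the primary one for that reason alone, and a reader could take the agreement as evidence that infection at dosing did not matter.

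**Working it through.** The plan gives no count of subjects expected to be removed, so there is no figure of its own to reproduce on this point. The related administrative result does reproduce: 8/223 = 3.6%, and Fisher's exact test on 8/223 versus 0/186 gives p = 0.009, in line with the reported p<0.01.

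**1. Timing.** The convention is in SAP 6.4: "Study day is defined as the number of days since the first study treatment administration+1". Nominal hours after dosing = (study day − 1) × 24.

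- End of the exclusion window: 72/24 + 1 = day 4.
- First scheduled swab, day 8: (8 − 1) × 24 = 168 hours.
- Early edge of its window, day 7: (7 − 1) × 24 = 144 hours.
- Clock times (dose late on day 1, swab early on day 7) can shorten this by at most 24 hours, to 120, which is still beyond 72.

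Scheduled swabs therefore exclude 0 subjects.

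**2. The remaining route.** Protocol 6.1.4 and footnote 4 to Table 3 call for an unscheduled swab when symptoms raise suspicion. SAP 6.4, Table 4, assigns unscheduled RT-qPCR results from day 2 onward to week 1. An early positive is therefore possible, but symptom, report, suspicion and swab must all fall by about day 4. A subject without symptoms has no planned swab in that period, so the asymptomatic half of the heading has no planned route to an exclusion.

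**3. A worked case.** Baseline swab negative on day 1, symptoms on day 2, first positive swab on day 8.

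- Under protocol 9.2.2.2 the symptom follows the last negative swab and precedes the first positive by 8 − 2 = 6 days, inside the 14-day limit. This is a primary event, with onset (2 − 1) × 24 = 24 hours after dosing.
- Under the sensitivity rule, onset is the swab, at 168 hours. The subject is kept.

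**4. Bounds from the administrative assessment** (protocol 3.2.5 and 3.2.6). Infections: 21 placebo + 9 active = 30. Symptomatic: 8 + 0 = 8, or 8/30 = 27%. The timing of those 8 is not reported, so the rule would have removed between 0 and 8 of them. The other 22 had no symptoms to prompt a swab. These subjects are outside the seronegative mFAS-A, so this is an indication only.

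**5. Illustration under assumptions.** Incubation is taken as lognormal with sigma 0.35 to 0.5. Infection time is uniform over the 1, 2, 3 or 4 days before dosing, with no symptoms at dosing. Treatment effect is ignored. Shares are of symptomatic pre-dose infections.

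| Median incubation (assumed) | Symptoms within 72 h | Swab within 72 h, 1-day delay | Swab within 72 h, 2-day delay |
|---|---|---|---|
| 5 days | 16–45% | 3–27% | 0–11% |
| 4 to 6 days | 7–64% | 1–41% | 0–18% |

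The first result column is the reach of a symptom-date rule. The other two are the reach of the present rule at two swab delays.

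**The case against.** The strongest reply is that the analysis concerns a symptomatic endpoint, and symptomatic subjects are the ones who get an early unscheduled swab. That stands. A reader might infer that the rule removes almost nobody, or that the analysis reproduces the primary result by construction. The documents support neither, because they give no count of early unscheduled positives, and the illustration allows a reach well above zero.

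A reader might also cite the day 8 positivity in protocol 3.2.6 (10.3% placebo, 5.4% active) to argue that most relevant events first appear at a visit the rule cannot reach. Those percentages count any infection, not the symptomatic endpoint. They also do not reconcile with the reported totals: 0.103 × 223 + 0.054 × 186 ≈ 23 + 10 = 33, against 30 infected. They should not be used to size this point.

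Third, much of the timing information is already planned. Symptomatic infection (broad term) at each week of the EAP is an other secondary endpoint for cohort A (SAP 4.5.3), and SAP 5.7.1 adds a Kaplan-Meier curve of time to first symptom. That also stands, and it makes a further split of the primary endpoint at week 1 largely redundant. Neither is designated as the check for infection at dosing, however, and neither repairs the rule.

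Finally, this is a supportive analysis. Infections present at dosing should be balanced on average by randomization, so the primary comparison is not invalidated. That is correct and limits the consequence to interpretation.

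**Conclusion.** The concern holds as a mismatch between what the analysis is headed to do and what its rule does. Three facts carry it: the rule uses only the RT-qPCR date, no scheduled swab falls before a nominal 144 hours, and protocol 9.2.2.2 dates symptomatic infection by the first symptom. The analysis can remove only subjects with an early unscheduled positive. It keeps those whose symptoms began within 72 hours but who first tested positive at the week 1 visit.

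Its size cannot be fixed: 0 exclusions through scheduled swabs, and an unknown number through symptom-triggered ones. With an assumed 5-day median incubation, the present rule would reach about 3–27% of symptomatic pre-dose infections at a 1-day swab delay and 0–11% at 2 days. A near-unchanged result would therefore say little about infection at dosing. The primary estimate, the alpha and the testing hierarchy are not affected. The point deserves correction because this is the only sensitivity analysis directed at the question.

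**What to change.** In SAP 5.7.1.1, with matching wording in protocol 11.4.3.1.1, define the date of early infection as the earlier of (a) first COVID-19 symptom onset, in subjects later confirmed RT-qPCR positive, using the onset definition in protocol 9.2.2.2, and (b) first positive RT-qPCR. Exclude subjects with that date within 72 hours of dosing. Report the number excluded in each arm and by which limb, so that the reach of the check is visible.

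Label the analysis supportive and state two limits. It remains a post-randomization exclusion on something treatment may influence. It also still cannot reach infections that are asymptomatic at 72 hours; under the 5-day illustration, 55–84% of symptomatic pre-dose infections would first show symptoms later than that. State that it is to be read with the by-week symptomatic infection endpoint and the Kaplan-Meier curve of time to first symptom.

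The cost is wording and a small programming change. Symptom start dates are already collected, so no new data are needed. SAP section 1 allows revisions based on blinded data before the first-step lock, and this change does not depend on any outcome result.

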5.7.1.2. Subgroup Analyses

To assess the homogeneity of the treatment effect across various subgroups, the primary analysis model with GEE approach will be applied to each subgroup if applicable; otherwise, the logistic regression model will be used. Odds ratio between the treatment groups and corresponding 95% CI will be provided, as well as the within-household correlation coefficient from GEE approach, within each subgroup.

The following subgroups of interest for Cohort A and Cohort B primary endpoints will be evaluated:

- Stratification age (years) group (≥ 12 to < 18 , ≥ 18 to < 50 , ≥ 50), and the additional age group: ≥ 12 to < 18 , and ≥ 18 years
- Sex
- Race (American Indian or Alaskan Native, Asian, Black or African American, Native Hawaiian or Other Pacific Islander, White and Other, where “Other” may include, for example, not reported, unknown, and multiracial, etc.) and an additional race group (White Hispanic or Latino, White not Hispanic or Latino, Black Hispanic or Latino, Back not Hispanic or Latino, and Other)
- Ethnicity (Hispanic or Latino, not Hispanic or Latino, and not reported or unknown)
- BMI (< 30 , ≥ 30)
- Number of study subjects in cohort B within a household (0, ≥ 1) (Cohort A only)
- Total household size including the household member(s) not participating this study (2, and > 2)
- Region (US, ex-US)
- Baseline high risk factor (Yes versus No) (as defined in Section 4.1)
- Healthcare worker (Yes/No) per exposure risk factor eCRF
- High viral load ($> 4 \log 10$ copies/ml) at baseline (Yes/No) (Cohort B only)

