#### 11.4.3.1.2. Subgroup Analyses

To assess the homogeneity of the treatment effect across various subgroups, the primary analysis model with GEE approach will be applied to each subgroup if applicable; otherwise, the logistic regression model will be used. Odds ratio between the treatment groups and corresponding 95% CI will be provided, as well as the within-household correlation coefficient from GEE approach, within each subgroup.

The subgroups of interest to be evaluated for cohort A primary endpoint include, but are not limited to:

- Stratification age group (years) ( $\geq 12$  to  $< 18$ ,  $\geq 18$  to  $< 50$ ,  $\geq 50$ ) and the additional age group:  $\geq 12$  to  $< 18$ ,  $\geq 18$  years
- Sex
- Race
- Ethnicity
- BMI ( $< 30$ ,  $\geq 30$ )
- Number of study subjects in cohort B within a household (0,  $\geq 1$ ) (cohort A only)
- Total household size including the household member(s) not participating this study (2, and  $> 2$ )
- Region (US, ex-US)

Additional subgroup analyses will be defined in the SAP.

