2.2. Sample Size and Power Considerations

2.2.1. Cohort A

The primary hypothesis is the reduction in the proportion of symptomatic RT-qPCR (broad-term) confirmed SARS-CoV-2 infections in seronegative subjects. To calculate the sample size to achieve at least 90% power for seronegative subjects in cohort A, it is assumed that the statistical hypothesis will be tested in a 2-sided test. Based on the administrative assessment results among 409 seronegative subjects in cohort A, an approximately 50% reduction of infection (symptomatic or asymptomatic) compared to placebo group and a 100% reduction of symptomatic infection compared to placebo group was observed. Due to the small sample size in the administrative assessment, it was assumed, for the purpose of assessing study power, that an approximately 50% reduction or greater in symptomatic infections compared to the placebo group will be expected for the final primary efficacy analysis.

In this household study design, the number of subjects per household, the correlation between subjects and symptomatic infection rates within a household are unknown. To detect a relative risk of 0.5 (i.e., 50% reduction of the assumed 10% attack rate in the placebo arm), equivalent to an odds ratio of 0.47, power was calculated compared to the p-value of 0.05 based on 2000

simulations in 1248 subjects from 430 households (i.e., assuming an average household size of 2.9 seronegative subjects). **Table 1** provides power calculations by varying degrees of correlation within household. In all cases, the power of the study is >90% using a generalized linear model with the generalized estimation equation (GEE) approach assuming a compound symmetry covariance matrix.

Table 1: Simulated Power for Household Design (1248 Subjects over 430 Households)

Placebo Attack Rate	REGN10933+ REGN10987 Attack Rate	Correlation within Household	Average Odds Ratio REGN10933+REGN10987 versus Placebo	Power
10%	5%	0.1	0.485	0.914
10%	5%	0.2	0.485	0.934
10%	5%	0.3	0.480	0.956
10%	5%	0.4	0.481	0.972
10%	5%	0.5	0.476	0.983
10%	5%	0.6	0.478	0.999

At least 1980 subjects will need to be enrolled in cohort A to have a minimum of 1248 seronegative subjects, assuming that 10% of subjects drop out, and 30% of subjects are seropositive at baseline.

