5.7.2. Adjustment for Multiple Comparison

The overall type I error will be controlled in each of seronegative mFAS-A and seronegative mFAS-B independently at 2-sided 5% significance level.

Seronegative mFAS-A Subjects

The overall type I error will be controlled for the primary hypothesis in Cohort A based on a 2-sided test at an alpha level of 0.05 as follows:

H0: There is no treatment difference between REGN10933+REGN10987 and placebo in the proportion of subjects with a symptomatic RT-qPCR confirmed SARS-CoV-2 infection during the EAP.

H1: There is a treatment difference between REGN10933+REGN10987 and placebo in the proportion of subjects with a symptomatic RT-qPCR confirmed SARS-CoV-2 infection during the EAP

If the primary efficacy endpoint in Cohort A is statistically significant, the alpha level of 0.05 will be released for the key secondary endpoints in Cohort A. The hierarchy testing sequence of key secondary endpoints is presented in the following table.

Table 2: Hierarchy Testing Sequence of Key Secondary Efficacy Endpoints in Seronegative mFAS-A

Key Secondary Efficacy Variables
Proportion of subjects with viral load >4 (log10 copies/mL) in NP swab samples during the EAP
Number of weeks of symptomatic RT-qPCR confirmed SARS-CoV-2 infection (broad-term) during the EAP
Number of weeks of high-viral load >4 (log10 copies/mL) in NP swab samples during the EAP
Number of weeks of RT-qPCR confirmed SARS-CoV-2 infection (regardless of symptoms) during the EAP
Proportion of subjects who have a RT-qPCR confirmed SARS-CoV-2 infection (regardless of symptoms) during the EAP
Proportion of subjects in placebo group with a RT-qPCR confirmed SARS-CoV-2 infection during the EAP with an index case participating in study R10933-10987-COV-2067 (comparison of those whose index cases receive REGN10933+REGN10987 vs placebo in R10933-10987-COV-2067)

Seronegative mFAS-B Subjects

The overall type I error will be controlled for the primary hypothesis in Cohort B based on a 2-sided test at an alpha level of 0.05 as follows:

H0: There is no treatment difference between REGN10933+REGN10987 and placebo in the proportion of subjects who subsequently develop signs and symptoms (broad-term) within 14 days of a positive RT-qPCR at baseline or during the EAP

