The secondary and exploratory continuous efficacy endpoints such as TWA, AUC, and maximum viral load (\log_{10} copies/mL) will be analyzed using the ANOVA including treatment group, region, and age group as fixed effects in the model. The continuous endpoints regarding change from baseline in cohort B (e.g., TWA of change/percent change from baseline) will be analyzed using the ANCOVA model with treatment group, region, and age group as fixed effects, and the relevant baseline values as covariate as well as treatment-by-covariate interaction. The REGN10933+REGN10987 group will be compared to the placebo group and corresponding least square of mean difference, standard error (SE) and 95% confidence interval will be provided. For

other endpoints with non-normal/skewed distribution (e.g. number of days of symptoms (strict-term, and CDC definition, etc.)), Van Elteren test will be used.

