6.5. Pooling of Centers for Statistical Analyses

Currently, the randomization is stratified by site. Since a potential differential treatment effect among countries may exist, region variable as a fixed effect factor will be included in the statistical analysis model. A subgroup analysis regarding region will also be performed for the primary efficacy endpoint. Results will also be summarized descriptively by country.

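### The plan sets out to assess homogeneity of the treatment effect across subgroups but includes no measure of the difference between subgroups

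*SAP*

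**What the plan says.** SAP 5.7.1.2 gives the purpose and the method in one sentence: "To assess the homogeneity of the treatment effect across various subgroups, the primary analysis model with GEE approach will be applied to each subgroup". The output follows: "Odds ratio between the treatment groups and corresponding 95% CI will be provided", together with the within-household correlation when GEE is used. Protocol 11.4.3.1.2 matches it: "the primary analysis model with GEE approach will be applied to each subgroup if applicable; otherwise, the logistic regression model will be used".

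On geography, SAP 6.5 says: "Since a potential differential treatment effect among countries may exist, region variable as a fixed effect factor will be included". The same section also plans a region subgroup analysis of the primary endpoint and descriptive results by country.

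The only interaction term in the plan concerns baseline values, not subgroups. For cohort B change-from-baseline endpoints, SAP 5.7.4 specifies an ANCOVA with treatment group, region and age group, "and the relevant baseline values as covariate as well as treatment-by-covariate interaction". Protocol 11.4.3.3 allows the same term where it is needed.

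Subgroup results carry no alpha. SAP 5.7.2 controls error for the primary and key secondary endpoints in each cohort "independently at 2-sided 5% significance level", and neither document gives a rule for interpreting a subgroup interval.

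SAP 5.7.1.2 lists eleven factors. One is for cohort A only and one for cohort B only, so each cohort has ten.

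**The concern.** Homogeneity is a statement about the contrast between subgroups: the odds ratio in one level divided by the odds ratio in another is 1. Fitting the model separately in each level estimates the two components but not the contrast or its uncertainty. A reader who wants to judge homogeneity is left to compare intervals by eye, and the usual shortcut is to note which of them exclude 1. That shortcut mostly reflects how many events each level has.

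Region shows the same gap. A region main effect adjusts for different attack rates; it cannot show that the treatment works differently by region. The planned region-specific estimates help, but they again stop short of a contrast.

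At stake is the reading of ten factors per cohort. SAP section 7 says first-step results may go into a submission to health authorities. A level with few events could be taken to lack benefit when the effect is the same, and a real difference would have no estimate attached to it.

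**Working it through.** **Inputs.** SAP 2.2.1 gives the planning effect for cohort A: "To detect a relative risk of 0.5 (i.e., 50% reduction of the assumed 10% attack rate in the placebo arm", described as "equivalent to an odds ratio of 0.47". It uses 1248 seronegative subjects; at 1:1 allocation that is 624 per arm. The significance level is two-sided 0.05. Subgroup shares are not in the documents, so 5% to 50% is assumed.

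**The plan's own figures first.**
- Odds ratio: (0.05/0.95)/(0.10/0.90) = 0.474, agreeing with 0.47.
- Power, comparison of two proportions, 624 per arm, 10% v 5%: 0.919, against 0.914 in SAP Table 1 at household correlation 0.1.
- Wald version: SE = √[1/(624×0.10×0.90) + 1/(624×0.05×0.95)] = √(0.01781 + 0.03374) = 0.227. |log OR| = 0.747. Power = Φ(0.747/0.227 − 1.96) = 0.908.

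The independence calculation is therefore a fair stand-in for the low-correlation case. The rows of Table 1 for correlations 0.2 to 0.6 were not re-simulated.

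**What separate intervals do when the effect is identical.** Both levels of a two-level factor were given true rates of 10% and 5%, with 200,000 simulated trials per row, independent binomials, a Wald interval for the log odds ratio, 0.5 added when a level had a zero cell, and no covariates or household correlation. The levels disagree when one interval lies wholly below 1 and the other does not. The interaction test compares the two log odds ratios: z = (log OR₁ − log OR₂)/√(V₁ + V₂).

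| Smaller level: share (n per arm) | Interval below 1, smaller level | Interval below 1, larger level | Levels disagree | Interaction test rejects | Interaction test rejects if smaller level truly has no effect |
|---|---|---|---|---|---|
| 5% (31) | 1.7% | 91.1% | 90% | 1.3% | 10% |
| 10% (62) | 9.9% | 89.3% | 82% | 2.4% | 21% |
| 20% (125) | 30.0% | 85.6% | 64% | 4.0% | 33% |
| 30% (187) | 43.9% | 80.5% | 54% | 4.7% | 40% |
| 50% (312) | 65.9% | 65.9% | 45% | 4.8% | 43% |

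The levels are independent, so disagreement can be checked by hand as s₁(1 − s₂) + s₂(1 − s₁). At 20%: 0.300×0.144 + 0.856×0.700 = 0.043 + 0.599 = 0.642. At 50%: 2×0.659×0.341 = 0.449.

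The last column is the power of the proposed contrast against complete loss of effect in the smaller level (10% v 10%). Check for equal halves: V₁ = 2/(312×0.09) = 0.0712; V₂ = 1/(312×0.09) + 1/(312×0.0475) = 0.1031; Φ(0.747/√0.1743 − 1.96) = Φ(−0.17) = 0.43.

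**Sparse cells.** With 31 per arm, the chance of no events is 0.95³¹ = 0.204 on active and 0.90³¹ = 0.038 on placebo, so at least one zero cell occurs with probability 1 − 0.796×0.962 = 0.23. The administrative assessment saw a placebo rate of 8/223 = 3.6% (protocol 3.2.5). With that rate halved on active, the figure is 1 − (1 − 0.982³¹)(1 − 0.964³¹) = 0.71, and disagreement across the same shares is 36% to 46%.

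**The case against.** The strongest reply is that the SAP plans no subgroup test. It gives no subgroup p-value, no alpha and no rule for setting an interval against 1. Side-by-side estimates with intervals are a recognised descriptive display, and a wide interval already tells the reader that a small subgroup is uninformative. On this view the disagreement rates describe a rule the sponsor never adopted, and at small shares they largely restate low subgroup power.

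Much of that stands. The rates describe a likely misreading, not a planned analysis, and the separate estimates are worth keeping. What does not fall away is that the stated purpose is homogeneity, and nothing planned estimates it.

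Some stronger readings are tempting but not supported:
- That the plan tests for no effect within each subgroup. It does not; that is only what comparing an interval with 1 would amount to.
- That SAP 6.5 answers a differential country effect with a main effect alone. It also plans region-specific estimates and country summaries; only the contrast is missing.
- That splitting households by age, sex or race would inflate the GEE type I error. SAP 6.6 simulated inflation under an extreme within-household correlation, the plan falls back to logistic regression, and several factors, such as region and household size, do not split households at all.
- That adolescents or ex-US subjects are most at risk of being misread. This needs subgroup sizes that the documents do not give.

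A further fair point is that an interaction test has little power here and cannot establish homogeneity. That is correct, and the remedy has to say so.

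**Conclusion.** The point holds in a limited form: the plan's aim is homogeneity, and neither document provides a between-subgroup contrast, including for region. If intervals are judged against 1, identical effects would appear discordant in about 45% of trials for equal halves and up to about 90% when the smaller level is 5% of subjects, while an interaction test would reject in 1% to 5%.

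These figures rest on the planning rates (10% v 5%), 1248 subjects, assumed subgroup shares, and no household correlation or covariate adjustment. Importance is moderate to low: the analyses are supportive, carry no alpha, and leave the primary conclusion untouched. This is an inexpensive improvement that should be made, not a flaw in the confirmatory analysis.

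**What to change.** Keep the within-subgroup odds ratios and CIs. In SAP 5.7.1.2 and protocol 11.4.3.1.2, add the following:

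- For each factor, fit the primary model to the whole seronegative mFAS-A with subgroup and treatment-by-subgroup terms. Do the same in mFAS-B if cohort B subgroups are retained. For region, already a covariate, only the treatment-by-region term is new; state this in SAP 6.5 as well.
- Report the ratio of odds ratios with its 95% CI and a nominal interaction p-value.
- Set a rule for sparse or zero cells, for example pooling small levels, or exact or penalised logistic regression.
- State that subgroup-specific significance will not be used to judge heterogeneity. State also that interaction power is low (about 10% to 43% even for complete loss of effect in the smaller level), so a non-significant result does not show homogeneity.

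Reconcile SAP 5.7.1.2, which plans cohort B subgroups, with the summary table in SAP 10.1, which marks cohort B subgroup analysis as not planned.

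The cost is some SAP wording and one extra model per factor. The interaction intervals will be wide, which is an honest picture of what the trial can say.
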